Primary hyperhidrosis is a pathological condition characterized by the idiopathic and excessive secretion of sweat beyond normal physiological demand and is localized at particular foci such as the face, axilla, palms of the hands, and soles of the feet. Patients seeking medical attention for hyperhidrosis often report disruptions to their professional and/or social lives due to sweating and subsequently experience many psychosocial difficulties, such as anxiety, social phobia, and depression. Therefore, a psychiatric explanation of causality is frequently offered for these patients during diagnosis. Excessive sweating is often mistakenly interpreted as a symptom of an anxiety disorder and can be cause for social embarrassment, exacerbating emotional stress and social avoidance. As currently constituted, the treatment of secondary psychosocial symptoms in primary hyperhidrosis is poorly understood and requires further investigation. We have previously collected data which showed substantial improvement in quality-of-life and psychometric evaluation of primary hyperhidrosis patients after surgical intervention. These data suggest the profoundly beneficial potential of medical treatments in terms of psychosocial deficits that were previously deemed primarily psychological. This study aims to evaluate the efficacy of miraDry R a novel non-invasive treatment system for primary hyperhidrosis of the axillae. This study hypothesizes a similar finding in the miraDry ® system as was observed for the surgical modality. If this prospective study finds a significant improvement in psychometric evaluation scores after miraDry ® treatment, then it would strongly suggest that patients seeking medical intervention to alleviate excessive sweating should experience marked improvement not only in their levels of sweating, but also in the psychopathological symptoms that they experienced pre-treatment. These findings could result in substantial advantage for hyperhidrosis patients in the future. It is well documented that primary hyperhidrosis can be an extremely debilitating condition so clearly a more robust understanding of the condition and effective evaluation of treatment options confers much tangible benefit for patients.

2. Objectives (include all primary and secondary objectives)

Primary Objective:

1. To evaluate the effectiveness of the miraDry ® treatment system for psychosocial functioning in patients heavily affected by axillary hyperhidrosis.

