Patients will be recruited from both the Johns Hopkins Department of Dermatology and Thoracic Surgery. The recruitment of these patients will occur during normal appointments and clinic visits at Johns Hopkins Hospital. Physicians in either department seeing hyperhidrosis cases will inform patients about the existence of the study. The International Hyperhidrosis Society reserves the right to notify persons regarding the existence of the research being conducted which would amount to no more than a link to the above website. Recruitment will not involve any media advertisements or flyers. The trial will be listed on clinicaltirals.gov and a link will provided to the Hopkins Center for Sweat Disorders website (http://www.hopkinsmedicine.org/sweat_disorders/).

Patients will be asked to complete the Hyperhidrosis Disease Severity Scale (HDSS) as a prescreening survey. The HDSS (below) is a diagnostic tool that qualitatively measures (Likert scaled 1-4) disease-specific severity of the patient's condition based on the degree to which daily activities are impacted:¹⁶

Hyperhidrosis Disease Severity Scale:

"How would you rate the severity of your hyperhidrosis?"

- 1. My sweating is never noticeable and never interferes with my daily activities
- 2. My sweating is tolerable but sometimes interferes with my daily activities
- 3. My sweating is barely tolerable and frequently interferes with my daily activities
- 4. My sweating is intolerable and always interferes with my daily activities

A score of 1 or 2 indicates mild or moderate hyperhidrosis while a score of 3 or 4 indicates severe hyperhidrosis. Patients scoring 3 or 4 on the HDSS who also meet the additional inclusion/exclusion criteria will be offered enrollment in the study. The HDSS has been validated for reliability by analysis in three studies and with correlative comparison to the Hyperhidrosis Impact Questionnaire (HHIQ), Dermatology Quality of Life Index (DLQI), and gravimetric sweat production measurements.¹⁶

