These potential participants will be approached directly following their clinical visits. For patients who then agree to participate in the study, written informed consent will be obtained. During the consenting process, the study will be thoroughly explained along with a description of the miraDry ® system and the predicted benefits and possible risks therein. No post-consent screening will be performed. No pre-consent Protected Health Information will be reviewed prior to the signing of consent.

Each participant will schedule an appointment with behavioral medicine and asked to complete additional, survey evaluations (all of which have been independently validated) as listed below. The same slate of surveys will be given at the second appointment and at follow-up.

Domain	Survey	Applicable Ages
Dermatology QOL	DLQI	>17 years
Broadband psychopathology	BASC	17-21 years
	BASC (college)	18-25 years
Anxiety	Zung Anxiety Self	>17 years
Depression	BDI-2	>17 years

Each participant will also schedule two miraDry ® treatment appointments approximatelythree months apart. The administration of miraDry ® treatments will take place at Greenspring located at [name].

At each of these treatment appointments, each participant will be asked to complete the above surveys reflecting their current states.

The miraDry ® treatment will be administered using a standard treatment procedure as follows:

- MiraDry system powered on and goes through a self check
- Patient positions self supine on exam table with bilateral axilla exposed by patient placing arms behind head
- Right & left axilla hair bearing area measured and appropriate water tatoo applied to axilla using isopropyl alcohol
- Hibiclens applied to right and left axilla and 1 percent lidocaine with epinephrine 1:100,000 injected at sites indicted by water tattoo
- Sterile KY jelly applied to right and left axilla
- New sterile biotip package opened and connected to MiraDry machine
- Procedure initiated using energy level 3-5, with the number of treatment sites dependent on the size of the hair baring area
- 2 reusable ice packs wrapped in paper towels given to patient to apply to axilla bilaterally

Additionally, study patients will be given the following post-procedure instructions:

- Continue ice packs for the next few days & to always wrap ice pack in a towel to prevent frost bite

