Lidocaine with epinephrine will be used as a local anesthetic to the treatment site. Additionally, hibliclens with chlorhexidine 4% is an antiseptic antibacterial agent routinely used to prevent the growth of bacteria on the skin and will be used at the treatment site. The drugs used in the study will be the same drug provided for the entire Johns Hopkins Department of Dermatology. There will not be a separate batch of this drug for the sole purposes of this study as this study is not a clinical trial and use of the drug is unlikely to interfere with study results.

b. Justification and safety information if FDA approved drugs will be administered for non-FDA approved indications or if doses or routes of administration or participant populations are changed.

N/A

c. Justification and safety information if non-FDA approved drugs without an IND will be administered.

N/A

7. Study Statistics

a. Primary outcome variable.

Pre- and post-treatment scores on the HHDS and other surveys described in Section 4a.

b. Secondary outcome variables.

Same as primary outcome variable. To compare miraDry ® treatment to surgical intervention, the data collected from the above surveys will be compared to previously collected pre- and post-operative survey data given to surgical patients.

c. Statistical plan including sample size justification and interim data analysis.

The cohort of axillary hyperhidrosis patients will be constituted by roughly 24 eligible individuals who meet the inclusion/exclusion criteria described in Section 5. This sample size was so determined based on the number of funded complete miraDry ® treatments. However, power analyses of existing clinical data would suggest 80% power to detect statistically significant decreases in anxiety and depressive symptoms with our proposed sample size. Data will be analyzed as it is collected for each study visit stage and again after follow-up for pre- vs. post- treatment comparison.

d. Early stopping rules.

Each patient has the right to discontinue their participation in the study at any time. All patients who wish to terminate participation in the study will have their request fulfilled effective immediately and indefinitely.

A participant may have their participation in the study discontinued if problems arise during the course of their involvement which require deviations from the approved protocol (section 8c).

8. Risks

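### All surveys are primary and are repeated as secondary, with analyses at each visit stage and after follow-up, but no deciding outcome, post-treatment timepoint, test or multiplicity rule is named

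*Combined protocol and SAP*

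**What the plan says.** **Outcomes.** Section 7a gives the primary outcome as "Pre- and post-treatment scores on the HHDS and other surveys described in Section 4a". HHDS appears to mean the HDSS. Section 7b says the secondary outcomes are the same and adds that "the data collected from the above surveys will be compared to previously collected pre- and post-operative survey data given to surgical patients".

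**Analysis.** Section 7c: "Data will be analyzed as it is collected for each study visit stage and again after follow-up for pre- vs. post- treatment comparison". Section 7d covers only the withdrawal or discontinuation of individual participants. No section gives a test, an alpha level or a multiplicity rule.

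**Power.** Section 7c sets the sample at about 24 by the number of funded treatments, and adds that analyses of existing data "would suggest 80% power to detect statistically significant decreases in anxiety and depressive symptoms with our proposed sample size".

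**Success condition.** The opening abstract begins its conclusion with "If this prospective study finds a significant improvement in psychometric evaluation scores".

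**Survey schedule.** The slate in Section 4a is DLQI, BASC (two age versions), Zung anxiety and BDI-2. Section 4b treats the behavioral medicine appointment as the initial psychometric evaluation, and Section 10a says baseline data are collected there. On later surveys, Section 4a says both "The same slate of surveys will be given at the second appointment and at follow-up" and "At each of these treatment appointments, each participant will be asked to complete the above surveys reflecting their current states". Section 4b places the follow-up survey between 6 months and 1 year after first treatment. Section 5 makes availability for the follow-up visit optional, and 4b allows phone, mail or electronic completion instead.

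**HDSS.** Section 4a: "Patients will be asked to complete the Hyperhidrosis Disease Severity Scale (HDSS) as a prescreening survey". It is not in the repeated slate, and Section 5 selects patients on a score of 3 or more.

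**The concern.** With every survey primary and none deciding, the analyst can choose after seeing the data which scale and which visit to present as the result. The abstract asks for significant improvement in scores without saying in how many scales, or when. A single significant survey could be reported as meeting that condition, and the abstract and Section 9 build benefit claims on it. These include the claim that patients might avoid psychiatric medication.

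Two listed instruments also do not fit the analysis as written. Section 7a needs a post-treatment HDSS score, but Section 4a describes the HDSS only as a prescreening tool. The BASC versions stop at age 25, while eligibility runs from 18 to 29, so some patients would have no listed BASC form.

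**Working it through.** **1. The plan's own figure.** The 80% power cannot be reproduced, because effect size, SD of change, alpha, sidedness and test are not given. It can be inverted. For a paired comparison with n = 24, the standardized change d (mean change divided by SD of change) that gives 80% power is approximately (z for alpha + z for power)/√n:

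- Two-sided 5%: (1.960 + 0.842)/√24 = 0.572; exact noncentral t gives 0.597.
- One-sided 5%: (1.645 + 0.842)/√24 = 0.508; exact noncentral t gives 0.523.

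The statement therefore implies a change of about 0.60 or 0.52 SD. The documents do not allow either to be confirmed or refuted.

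**2. False-positive chance under the any-one-survey reading.**

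- From the documents: about 24 patients; four repeated survey domains, of which three are psychometric (BASC, Zung, BDI-2) and one is quality of life (DLQI); two post-treatment survey points (second treatment visit and follow-up).
- Assumed: paired t-tests at two-sided 5%, no true mean change, 24 complete pairs, correlation 0.3 to 0.7 between scales and 0.5 between stages.
- Counted: decreases only, so the nominal rate per test is 2.5%.
- Excluded: the HDSS. Selection on 3 or more makes a fall likely without any treatment effect, so a zero-change null does not suit it.

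Under independence the chance for k tests is 1 − 0.975^k: 7.3% for k = 3, 9.6% for 4, 14.1% for 6 and 18.3% for 8. Simulation with the assumed correlations (200,000 trials per cell) gives:

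| Surveys | Follow-up only | Follow-up and second treatment visit |
|---|---|---|
| Three (BASC, Zung, BDI-2) | 5.6-6.9% | 9.9-12.3% |
| Four (adding DLQI) | 6.6-8.8% | 11.6-15.5% |

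If BASC is available for only 12 to 16 patients (an assumption reflecting the age gap), the ranges over three and four surveys are 5.9-8.9% and 10.4-15.7%. The conclusion does not change.

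**3. Effect of a rule.** Holm at overall two-sided 5% at one timepoint brings the favourable false-positive chance to 2.2-2.5% with two primaries and 2.0-2.4% with three.

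**4. What the rule costs in power.** At d = 0.597 on every primary outcome, with 24 pairs and the same correlations:

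| Primaries | First-step power (alpha/k) | Average per-outcome Holm power | At least one success |
|---|---|---|---|
| One, unadjusted | 80% | – | 80% |
| Two | 70% | 75-77% | 81-88% |
| Three | 64% | 72-73% | 82-91% |

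The first-step column is the Bonferroni value and understates Holm.

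**5. Missing follow-up.** Detectable d at 80% power, with a loss of four pairs as an assumed illustration:

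| Complete pairs | Unadjusted | First Holm step, two primaries | First Holm step, three primaries |
|---|---|---|---|
| 24 | 0.60 | 0.67 | 0.71 |
| 20 | 0.66 | 0.74 | 0.78 |

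**The case against.** **Scores in the plural.** The abstract can be read as asking for a pattern across scales. That is fair. The error rates above belong to the any-one-survey reading only. But the plan does not exclude that reading, and it states no rule for a pattern either.

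**Anxiety and depression as implied primaries.** The power sentence names these two domains. Section 7a does not, and the primary objective, psychosocial functioning, is broader. The sentence suggests a sensible choice of primaries but does not make it.

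**Stage analyses may be descriptive.** They may, but 7c does not say so. The inflation at follow-up alone remains in any case. A reader might go further and infer repeated interim testing with early stopping. The documents contain no efficacy stopping, so the risk is selective reporting among looks.

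**Baseline.** A reader might infer that the pre-treatment score is undefined. Sections 4b and 10a place it at the behavioral medicine appointment. What is unstated is how the survey at the first treatment visit is used.

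**Larger inflation figures.** Counting both directions and including the HDSS gives 15-21% for five surveys at one timepoint. That overstates the problem: only a favourable change could meet the condition, and the zero-change null does not suit the HDSS.

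**The uncontrolled design matters more.** It limits any causal claim whatever is done about multiplicity. It does not excuse an undefined primary analysis.

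**Conclusion.** The concern holds: the plan names no deciding outcome, post-treatment timepoint, test or multiplicity rule. If one significant survey is enough, the chance of a favourable false positive is about 6-9% at follow-up only and 10-16% with the second treatment visit added, against 2.5%. These figures depend on the assumed tests, 24 complete pairs and correlations, none of which the documents give.

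A reader might also infer that the 80% power is wrong. The documents support only that it is unverifiable. Nor would controlling multiplicity show that treatment caused an improvement. It makes the test interpretable, but regression to the mean and natural change remain. This should be fixed; wording is enough.

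**What to change.** **Section 7a.** Name a small primary set at one timepoint. One example is change from the behavioral medicine baseline to the follow-up survey in Zung anxiety and BDI-2. These are the domains of the power statement, and both are listed for all eligible ages. Test once, after the last follow-up, by two-sided paired t-test with Holm at overall 5%. A single primary, a fixed testing order, or adding DLQI to the Holm family would also cure the defect. Name one target follow-up time with a window inside the 4b range, and use one survey per patient. Because the follow-up visit is optional, state how missing follow-up surveys are handled and report the number of complete pairs. State how the first-treatment-visit survey is used.

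**Section 7b.** Make the other surveys and the surgical comparison secondary, outside the primary family. Label the visit-stage analyses descriptive. Reconcile 7a with 4a on whether the HDSS is repeated; if it is, report it descriptively only. Reconcile the BASC ages with the 18-29 eligibility.

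**Section 7c.** Restate power for the chosen primaries with effect size, SD of change, alpha, sidedness, test and expected complete pairs. If these are unavailable, give the detectable effects in step 5 of the working for 24 and 20 pairs.

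**Cost.** Protocol wording only, with no added patients or visits. The other surveys lose primary status, and the stated per-outcome power falls as in step 4.

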- Keep underarms clean using liquid soap to clean the underarms twice a day until the underarm is healed from procedure
- Do not shave underarm until underarm tenderness is resolved and any wounds are healed
- Do not apply antiperspirant or deodorant until underarm tenderness is resoled and any wounds are healed
- Wear loose clothing for 5-7 days to prevent any underarm irritation
- Apply an over the counter antibiotic ointment twice daily to the underarms for 1 week
- An anti-inflammatory over-the-counter drug such as ibuprofen can help manage pain and reduce swelling. It should be taken according to package instructions and as long as there are no contraindications to patient taking this medication.

b. Study duration and number of study visits required of research participants.

This study should take approximately 2 years to complete. Participants will be required to be present for at least 4 study visits. The first visit will be for consultation and to determine whether the patient meets the inclusion/exclusion criteria. Then each consented patient will schedule a behavioral medicine appointment for initial psychometric evaluation. This is followed by 2 visits to administer the miraDry ® treatment, spaced approximately 3 months apart. A follow up survey will take place roughly between 6 months and 1 year after the first treatment visit. The follow up visit is optional because the survey will be administered over phone, through the mail, or electronically if the patient is unavailable for study visit.

c. Blinding, including justification for blinding or not blinding the trial, if applicable.

This study will compare patient psychometric data at the time of before treatment/consultation to corresponding post-treatment information. Researchers will therefore be blinded to a patient's pre-treatment information when collecting post-treatment data via telephone call or in any situation involving direct patient interaction to eliminate potential bias when soliciting, recording, or analyzing study data.

d. Justification of why participants will not receive routine care or will have current therapy stopped.

N/A

e. Justification for inclusion of a placebo or non-treatment group.

N/A

f. Definition of treatment failure or participant removal criteria.

N/A

g. Description of what happens to participants receiving therapy when study ends or if a participant's participation in the study ends prematurely.

N/A

5. Inclusion/Exclusion Criteria

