a. Medical risks, listing all procedures, their major and minor risks and expected frequency.

Most of these side effects can last from a few days to a few weeks following treatment. Others can last from one to several months or longer as noted.

The most common side effects observed within or near the treatment area follow below.

- Swelling/tightness in the treated area
- Discomfort, tenderness or pain in the underarm when touched, usually treatable with non-prescription medications such as ibuprofen
- Redness from the device suction
- Bruising at the numbing injection sites
- Bumps under the treated area (can last for several months)
- Temporary altered sensation or tingling in small areas of the treated skin or upper arm (can last for several months)
- Partial or total underarm hair loss (can last for several months)

Other less common side effects include:

- Swelling in the adjacent arm or torso (usually lasting a few days)
- Hyperpigmentation (darkening of skin) in the treatment area
- Soreness in the shoulders or arms due to positioning of the arms during the procedure
- Numbness or tingling in the arm due to the anesthesia (usually less than 24 hours)
- Shaking due to epinephrine in the anesthesia (usually lasting less than 24 hours)
- Tight band in the underarm (gradually resolves)
- Small blisters or rashes in the treatment area

There have been rare reports of:

- Altered sweating elsewhere on the body
- Decrease in strength in the arm or fingers that gradually goes away (but can last for several months)
- Pain in the underarm requiring prescription medications
- Infection
- Burns

b. Steps taken to minimize the risks.

Risks associated with the system are usually rare or transient. Patients will be made aware of the aforementioned risk factors.

c. Plan for reporting unanticipated problems or study deviations.

Any problems involving the medical risk factors listed in section 8a are subject to the early stopping protocol explain in section 7d. Any patient who wishes to discontinue participation will have that request honored immediately and his/her standard treatment will resume unaffected.

The study team will not continue the protocol with a particular patient if a situation arises whereby the study protocol would require modification for continuation with said patient.

Unanticipated problems and potential study deviations will be reported to the JHM IRB.

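### Sections 7d and 8c end participation as a whole, so a participant removed between the two treatments would have no post-treatment score

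*Combined protocol and SAP*

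**What the plan says.** Section 7d (early stopping rules) first gives participants the right to leave, then adds a rule for the study team: "A participant may have their participation in the study discontinued if problems arise during the course of their involvement which require deviations". Section 8c is firmer: "The study team will not continue the protocol with a particular patient if a situation arises whereby the study protocol would require modification for continuation". Section 8c also says that problems involving the medical risks listed in 8a "are subject to the early stopping protocol explain in section 7d". Both rules refer to study participation or to the protocol as a whole. Sections 4f (removal criteria) and 4g (premature end of participation) are marked not applicable.

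The surveys belong to the protocol. Section 4a gives a baseline set at the behavioral medicine appointment and then states: "The same slate of surveys will be given at the second appointment and at follow-up". It adds: "At each of these treatment appointments, each participant will be asked to complete the above surveys reflecting their current states". Section 4b has the two treatments "spaced approximately 3 months apart" and the follow-up survey 6 to 12 months after the first treatment. At follow-up, "the survey will be administered over phone, through the mail, or electronically if the patient is unavailable for study visit". Section 7a makes the pre- and post-treatment survey scores the primary outcome.

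**The concern.** When a problem prevents a participant from continuing the protocol unchanged, the written rules end everything, including outcome collection. If that happens between the two treatments, the participant has been treated but contributes no post-treatment outcome. The pre/post comparison could then be limited to people who had no such problem.

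The study has one arm and about 24 participants, so no control group would show whether the loss is selective. If removed participants improve less than the others, the reported benefit is too large. If they improve equally there is no bias, and if they improve more the benefit is understated. The documents do not settle which applies, and without the surveys nobody could find out afterwards.

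**Working it through.** **1. Which scores would exist.** Setting the removal rules (7d, 8c) against the schedule (4a, 4b):

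| Survey | Timing | Available if removed between treatments 1 and 2? |
|---|---|---|
| Behavioral medicine visit | before treatment 1 | yes |
| Treatment visit 1 | day of treatment 1 | yes, but a same-day score is not a meaningful outcome |
| Treatment visit 2 | about 3 months after treatment 1 | no |
| Follow-up | 6 to 12 months after treatment 1 | no |

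The number of usable post-treatment scores is 0, so there is no pre/post pair. After treatment 2 only the follow-up survey remains, and the visit 2 score already exists, so exposure there is small.

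**2. How removal could arise.** Side effects alone do not trigger it; a problem must require a deviation or modification. One plausible route, which is an inference: 8a lists effects that may persist for several months (bumps, altered sensation, hair loss and, rarely, reduced arm or finger strength). These could still be present when treatment 2 is due, and delaying or changing it might count as a deviation.

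**3. Effect on the estimate.** Let k be the number removed out of 24 and f their mean improvement as a fraction of the completers' improvement. Relative to the all-treated mean change, the completers-only mean change differs by

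24 / ((24 - k) + k × f) - 1.

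The documents give neither k nor f; both are assumed.

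| f | k = 1 | k = 2 |
|---|---|---|
| 1 | 24/24 - 1 = 0% | 24/24 - 1 = 0% |
| 0.5 | 24/23.5 - 1 = +2.1% | 24/23 - 1 = +4.3% |
| 0 | 24/23 - 1 = +4.3% | 24/22 - 1 = +9.1% |
| 1.5 | 24/24.5 - 1 = -2.0% | 24/25 - 1 = -4.0% |

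**4. Effect on power.** Section 7c states 80% power with about 24 participants. This cannot be reproduced, because the test, alpha, sidedness, effect size and standard deviation are not given. For scale, assume a paired t-test at 0.05. Power is the probability that a noncentral t variable with n - 1 degrees of freedom and noncentrality d × √n exceeds the critical value. Solving for 80% at n = 24 gives the standardized change d.

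| Test | d | n = 24 | n = 23 | n = 22 |
|---|---|---|---|---|
| Two-sided 0.05 | 0.597 | 80% | 78% | 76% |
| One-sided 0.05 | 0.523 | 80% | 78% | 77% |

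**5. Power if all 24 are surveyed.** This was simulated 400,000 times with standard deviation of change 1, two-sided 0.05, mean change 0.597 in completers and f × 0.597 in the k removed.

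| f | k = 1 | k = 2 |
|---|---|---|
| 1 | 80% | 80% |
| 0.5 | 78% | 76% |
| 0 | 76% | 72% |
| 1.5 | 81% | 83% |

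**The case against.** **The loss is read into the text.** Nothing expressly forbids a follow-up survey after treatment stops, 7d is permissive, and 4b already has a remote route. It is true that no sentence bans the survey. But 8c is not permissive, and surveying someone who has skipped treatment 2 is itself a modified protocol. The remote route is offered to patients who cannot attend follow-up and is nowhere extended to removed participants.

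**The route to removal is narrow.** The treatment interval is approximate, the energy level is a range of 3 to 5, and the number of treatment sites varies with the area. A short delay or a lower setting may therefore not be a deviation. The reference from 8c to 7d may also largely concern patients who choose to leave, whom the fix cannot recover if they refuse data collection. Both points stand and limit how often the problem would arise. Sections 8b and 8d also describe the risks as infrequent or short-lived.

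**The effect is small and its direction unknown.** This stands for the illustrated range. It does not remove the fact that the missing data could never be checked.

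**The target may be the full course.** Section 5 enrolls only people available for both treatments, and 7c sized the study by funded complete treatments. A participant with one treatment does not directly answer a two-treatment question. This is fair, and it is why the choice of main estimate belongs to the sponsor. Collecting the surveys keeps either choice open.

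**It is part of a wider gap.** Voluntary withdrawal, optional follow-up attendance and the lack of a missing-data method matter too. That is so, but this path is created by the protocol's own rule and can be closed by rewording it.

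**Conclusion.** The concern holds. As written, 7d and 8c end surveys together with treatment, and removal between treatments 1 and 2 leaves no post-treatment score. The number affected is probably small. With an assumed 1 or 2 of 24 removed, the completers' mean change is off by between -4.0% and +9.1% as f runs from 1.5 to 0, and by nothing if improvement is equal. The largest figure requires two removals and no improvement in either. The power loss of 2 to 4 points is minor and rests on an assumed test and alpha. What matters is an outcome-related gap that cannot be filled later. The text and schedule are clear; how often removal would occur is inference, so confidence is medium. The change should be made, but the gap does not invalidate the design.

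**What to change.** - Amend 7d and 8c to say that stopping treatment does not stop the surveys unless the participant withdraws from data collection. When to stop treatment remains the sponsor's decision.
- Collect the remaining surveys at their planned times by the phone, mail or electronic route in 4b. Both times can be counted from treatment 1, so they remain defined if treatment 2 is not given.
- Record separately the date and reason for stopping treatment and for stopping surveys.
- Report the pre/post change for everyone with at least one treatment and a post-treatment survey, alongside the two-treatment completers. The sponsor should state beforehand which is the main estimate.

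The cost is protocol wording and a few remote surveys. Participants who withdraw from data collection are still lost. The all-treated estimate may be smaller and its power lower: down to 72% in the worst case shown, with two removed and no improvement in either. It stays at 80% if they improve equally and rises to 81% or 83% if they improve 1.5 times as much.
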